11.3.1. Adverse Event

An AE is defined as any untoward medical occurrence associated with the use of a drug in humans, whether or not considered drug related.

An AE may be any unfavorable and unintended sign (including an abnormal laboratory finding), symptom, or disease temporally associated with the use of an IP, whether or not considered causally associated with the use of the IP. Any abnormal laboratory value, vital sign result, or ECG or X-ray finding deemed clinically significant by the Investigator, regardless of causal relationship, must be reported as an AE. A clinical diagnosis, rather than the changes in laboratory analyte or other assessment, should be recorded (eg, anemia rather than low hemoglobin value).

Examples of AEs include the following:

- Significant or unexpected worsening or exacerbation of the condition or indication under study (eg, acute COPD exacerbation as diagnosed from signs and symptoms such as cough frequency and severity, sputum production, dyspnea).
- Exacerbation of a chronic or intermittent pre-existing condition, including either an increase in frequency or intensity of the condition (eg, abnormal physical examination finding).
- Signs, symptoms, or clinical sequelae of a suspected interaction.
- Signs, symptoms, or clinical sequelae of a suspected overdose of the IP or a concurrent medication (overdose per se should not be reported as an AE or SAE, unless nonserious or serious sequelae [respectively] occur).
- The following abnormal laboratory results:
 - Any laboratory abnormality suggestive of a new disease/organ toxicity or a worsening of a pre-existing condition.
 - Any laboratory abnormality that required the participant to have IP interrupted or discontinued.
 - Any laboratory abnormality that required the participant to receive specific treatment for the lab abnormality.
 - Any laboratory abnormality that required additional monitoring and follow-up visits.
 - Any laboratory abnormality requiring further diagnostic investigation.

The following examples are not considered AEs:

- Medical or surgical procedure (eg, endoscopy, appendectomy), although the condition that leads to the procedure is an AE.
- Anticipated day-to-day fluctuations of pre-existing disease(s) or condition(s) (including laboratory values) present or detected at the start of the trial that do not worsen.
- The disease or disorder being studied, or expected progression, signs, or symptoms of the disease or disorder being studied, unless they become more severe or occur with a greater frequency than expected for the participant's condition.

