5. OBJECTIVES AND ENDPOINTS

The primary, secondary, and exploratory objectives and endpoints are provided in [Table 2](#).

Table 2: Objectives and Endpoints

Primary Objective	Primary Endpoint

 To evaluate the efficacy of rademikibart compared to placebo as an adjunct to standard therapy on the treatment failure rate within 28 days after randomization in participants with COPD and an eosinophilic phenotype experiencing an acute COPD exacerbation. 	
 Treatment failure rate within 28 days after randomization.
Secondary Objectives	Secondary Endpoints

 To evaluate the efficacy of rademikibart compared to placebo as an adjunct to standard therapy on subsequent COPD exacerbations in participants with COPD and an eosinophilic phenotype experiencing an acute COPD exacerbation. 	
 Rate of new moderate and severe COPD exacerbations over the 28 days after randomization. Time to the first new moderate or severe COPD exacerbation in the 28 days after randomization. Mean CFB in clinical respiratory symptoms of COPD using the E-RS: COPD comprised in the EXACT-PRO through Week 1, Week 2, and Week 4. Absolute CFB in post-BD FEV₁ at Day 3, Week 1, and Week 4.

 To evaluate the safety of rademikibart compared to placebo when administered as an adjunct to standard therapy in participants with COPD and an eosinophilic phenotype experiencing an acute COPD exacerbation. 	
 Incidence of AEs, including SAEs, AESIs, and DILI reported. Incidence of UADEs. Incidence of injection site reactions. Changes in safety laboratory parameters. Changes in vital signs, physical examinations, and ECG parameters.
Exploratory Objectives	Exploratory Endpoints

 To further evaluate the efficacy of rademikibart compared to placebo as an adjunct to standard therapy on subsequent COPD exacerbations in participants with COPD and an eosinophilic phenotype 	
 Proportion of participants with at least 1 moderate or severe acute COPD exacerbation (subsequent to the index acute COPD exacerbation) through Week 4 and Week 8.

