13.2. Sample Size Determination

Approximately 160 participants with COPD exacerbation will be randomized using 1:1 allocation ratio to rademikibart 600 mg SC or placebo. The sample size calculation is based on the statistical analysis of the primary endpoint of treatment failure rate.

To account for a 5% dropout rate, approximately 160 participants will be randomized to ensure that 152 participants are evaluable. Assuming treatment failure rates of 22.5% for the rademikibart group and 45% for the placebo group up to 28 days after randomization, this sample size will provide at least 80% power to detect a difference at a 2-sided Type I error rate of 5%. Conditional power will be calculated during the IA and the final sample size will be determined according to the prespecified rules.

To ensure that the sample size is reasonably sufficient, an unblinded sample size re-estimation will be conducted when approximately the first 80 participants in total have had the opportunity to complete the trial or discontinue early (ie, no ongoing participants will be included in this sample size re-estimation procedure). The unblinded sample size re-estimation procedure for this trial will not allow for a reduction in the planned sample size or an increase in sample size greater than 40 participants per group (80 participants total). This sample size re-estimation procedure will be conducted by a statistician who is not associated with the conduct or final analysis of the trial. No penalty will be applied to the p-values or confidence intervals for assessing treatment difference from placebo due to this sample size re-estimation procedure. The independent statistician and DMC will recommend to the Sponsor any changes required to the sample size. Results from the IA will be communicated to a limited number of the Sponsor's senior management team who are independent of the clinical trial team and will be identified in the unblinding plan before the IA is performed.

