13.4.8.1. Adverse Events

AEs will be coded using the Medical Dictionary for Regulatory Activities. TEAEs are defined as any AEs that occur or worsen during the Treatment Assessment Period, whether or not considered related to the treatment. The incidence of TEAEs will be presented overall, by system organ class, and by preferred term (PT) for each treatment group. Incidence of TEAEs by severity and relationship to IP will also be presented for each treatment group. Deaths, SAEs, AESIs and AEs resulting in discontinuation from the IP or trial will be summarized by treatment group.

In addition, AEs occurring during the Follow-up Period will be summarized for participants followed during that period.

A listing will be provided for all participants who experience a TEAE, SAE, discontinue IP or trial prematurely because of AEs, and temporarily interrupt IP because of AEs. AESIs will also be listed.

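### Section 11.3.1 classes a significant but expected COPD exacerbation both as an adverse event and as not one, so sites can record the same relapse differently

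*Protocol*

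**What the plan says.** Protocol section 11.3.1 (Adverse Event) has two lists. The first gives examples of adverse events and includes "Significant or unexpected worsening or exacerbation of the condition or indication under study (eg, acute COPD exacerbation as diagnosed from signs and symptoms" (the examples that follow are cough, sputum and dyspnea). The second gives examples that are not adverse events and includes "The disease or disorder being studied, or expected progression, signs, or symptoms of the disease or disorder being studied, unless they become more severe", or more frequent, than expected for that participant.

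The endpoint that depends on this is the secondary safety endpoint in section 5: "Incidence of AEs, including SAEs, AESIs, and DILI reported". Section 13.4.8.1 sets the window: "TEAEs are defined as any AEs that occur or worsen during the Treatment Assessment Period, whether or not considered related to the treatment". It also sets the display: "The incidence of TEAEs will be presented overall, by system organ class, and by preferred term (PT) for each treatment group".

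Exacerbations are collected separately as efficacy data to Day 56 (section 10.2), with onset, healthcare visit, treatment and resolution. That section does not say whether such an event is also entered as an adverse event.

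**The concern.** The first list joins its two conditions with *or*: significance alone is enough, so an expected exacerbation qualifies if it is significant. The second list removes expected manifestations of the studied disease and does not mention significance. A relapse that is significant but of expected severity and frequency therefore meets both lists.

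This is not a rare case here. Section 4.3.5 describes a population at high risk of further exacerbations. Inclusion criterion 5 requires an exacerbation treated with systemic corticosteroids in the previous 12 months. Section 4.1 says exacerbations cluster and cites readmission of about 20% of hospitalized patients within 30 days. An investigator can reasonably call an early relapse expected, and the protocol gives no expected rate or severity against which to apply the exception.

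With about 50 sites, the convention may vary. If the drug works, relapses will be unequal between arms, so the recording convention can move the overall AE and SAE comparison for a reason unrelated to tolerability. The analysis cannot repair this later, because a relapse never entered as an AE does not reach the AE tables.

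**Working it through.** **Step 1. Set the two lists side by side.**

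| New COPD exacerbation after dosing | AE example list | Not-an-AE list | Agreement |
|---|---|---|---|
| More severe or more frequent than expected | AE | AE (exception applies) | Yes |
| Significant, of expected severity and frequency | AE | Not an AE | **No** |
| Neither significant nor unexpected | Not named | Not an AE | Yes |

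The conflict is confined to the middle row.

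**Step 2. Look for a rule elsewhere.**
- Section 10.2 defines and collects exacerbations but does not link them to AE recording.
- Section 11.3.2 applies the seriousness criteria to something that is already an AE or suspected adverse reaction, so it does not decide the prior question.
- Section 11.6 requires all AEs to be recorded but does not say whether a relapse is one.
- Sections 13.4.8 and 13.4.8.1 give no rule for exacerbations in the AE tables.

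**Step 3. Check what the planning rates measure.** Section 13.2 states: "Assuming treatment failure rates of 22.5% for the rademikibart group and 45% for the placebo group up to 28 days after randomization".
- Dropout: 160 × (1 − 0.05) = 152 evaluable, or 76 per arm.
- Power at 76 per arm, two-sided 5%: 84.2% by the pooled normal approximation and 80.0% by Fisher's exact test. The stated figure of at least 80% is reproduced, and the sample size is not in question.
- Expected treatment failures: 0.45 × 76 = 34.2 on placebo and 0.225 × 76 = 17.1 on rademikibart, together 51.3 of 152 (33.75%).

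These counts are treatment failures as defined in section 10.1. That composite also takes in death from any cause, unscheduled visits and treatment intensification. They do not bound the middle row of the table:
- The ambiguous number can be lower. Deaths from any cause count as failures, and worse-than-expected exacerbations are AEs under both lists.
- The ambiguous number can be higher. Mild exacerbations (section 10.2) need not be failures.

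**Step 4. Illustrate the mechanism.** The protocol gives no AE rate, so this step rests on assumptions: a background AE incidence *b* of 20% to 60%, equal in both arms and independent of failure; treatment failures as a stand-in for the ambiguous events; and the same share *s* of them recorded as AEs in each arm. With failure rate *f*:

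incidence = b + (1 − b) × s × f, so the difference between arms = (1 − b) × s × (0.45 − 0.225).

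| b | s = 0 | s = 0.5 (placebo vs drug) | s = 1 (placebo vs drug) | Difference at s = 1 |
|---|---|---|---|---|
| 20% | 20% both | 38.0% vs 29.0% | 56.0% vs 38.0% | 18 points |
| 40% | 40% both | 53.5% vs 46.8% | 67.0% vs 53.5% | 13.5 points |
| 60% | 60% both | 69.0% vs 64.5% | 78.0% vs 69.0% | 9 points |

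The direction is clear: the more relapses are recorded, the better the drug looks on overall AE incidence. The size depends on the assumptions and is not an estimate for this trial.

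**The case against.** The strongest reply is that the lists can be read together. Section 10.2 defines an exacerbation as clinically significant worsening, which fits the AE example. A neighbouring exclusion covers day-to-day fluctuation that does not worsen. On this reading the named event governs, and the exclusion covers background COPD and residual symptoms of the index event. It is a sensible reading and probably the intended one. The text does not say so, however, and an investigator who regards a relapse as expected can rely on the exclusion as written.

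Four stronger inferences are tempting, and the protocol does not support them:
- *That the section contradicts itself outright on exacerbations.* The lists agree for those worse or more frequent than expected.
- *That up to 45% versus 22.5% of participants are in doubt.* Those are planning rates for a composite efficacy endpoint and neither an upper nor a lower bound. Nor does a group rate settle what is expected for an individual, which is what the exclusion asks.
- *That hospitalized relapses will escape SAE reporting.* Admission is a seriousness criterion, and a relapse needing admission will often meet the more-severe exception. What remains is that some could be judged expected and left out.
- *That an excess of other AEs would be hidden.* Tables by preferred term keep COPD terms on their own rows, so dilution is limited to the overall TEAE and SAE lines. The relapses themselves also remain in the efficacy data.

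It is also fair that table layout belongs to the SAP, so the absence of a split table is not a fault in the protocol. The recording rule is different, because sites apply it before any analysis.

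**Conclusion.** The point holds in a limited form. For a significant but expected COPD exacerbation, section 11.3.1 gives two answers, and nothing else in the protocol chooses between them. The consequence is inconsistent recording across sites, which affects overall AE and SAE incidence and whether some relapses enter SAE reporting. The primary analysis and the sample size are untouched.

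The number of participants affected cannot be derived from the protocol. The illustrative shift of 9 to 18 points, if every failure were recorded rather than none, rests on the assumed background rate, on independence, and on failures standing in for ambiguous events. It shows the mechanism only. The defect is moderate and cheap to remove, and it is best corrected before much data has been entered.

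**What to change.** Reconcile the two lists in section 11.3.1 with one recording rule. For example: the exclusion for the studied disease covers background COPD and residual symptoms of the index exacerbation, but not a new protocol-defined exacerbation with onset after dosing. Such an event is recorded as an AE, and as an SAE if it meets a seriousness criterion in section 11.3.2. Another convention would also serve, provided it is single and explicit.

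As a companion summary, show overall TEAE and SAE incidence with and without COPD-exacerbation preferred terms; the SAP can carry this.

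The cost is a sentence in section 11.3.1, some extra AE entries and one extra table row. Sites already collect the onset, visit, treatment and resolution of each exacerbation, so the added burden is small. The change concerns recording only and alters no treatment.

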11.3.2. Serious Adverse Event

An AE or suspected adverse reaction is considered “serious” if, in the view of either the Investigator or Sponsor, it results in any of the following outcomes:

- Death.
- A life-threatening AE (ie, presented an immediate risk of death from the event as it occurred. This criterion is not intended to include an AE that, had it occurred in a more severe form, might have caused death.)
- Inpatient hospitalization or prolongation of existing hospitalization.
- A persistent or significant incapacity or substantial disruption of the ability to conduct normal life functions.
- A congenital anomaly/birth defect.
- Important medical events that may not result in death, be life-threatening, or require hospitalization may be considered serious when, based upon appropriate medical judgment, they may jeopardize the participant and may require medical or surgical intervention to prevent one of the outcomes listed in this definition. Examples of such medical events include allergic bronchospasm requiring intensive treatment in an emergency room or at home, blood dyscrasias or convulsions that do not result in inpatient hospitalization, or the development of drug dependency or drug abuse.

The following events do not meet the definition of an SAE: hospitalization for elective treatment of a pre-existing condition that does not worsen from baseline, hospitalizations for a standard procedure for IP administration, routine monitoring of the studied indication not associated with any deterioration in condition, social or convenience admission to a hospital, prolongation of a hospitalization for social or convenience reasons not associated with the occurrence of an AE, or hospitalization or an emergency room visit that lasts less than 24 hours that does not meet the criteria of an important medical or a life-threatening event.

11.3.3. Adverse Event of Special Interest

An AESI may be serious or non-serious and is one of scientific and medical concern specific to the Sponsor's product mechanism of action, for which ongoing monitoring may be appropriate. Such an event might warrant further investigation to characterize and understand it and rapid communication by the trial Sponsor to other regulatory authorities may also be warranted.

For this trial, AESIs shall include:

- Conjunctivitis
- Keratitis
- Severe injection site reactions persisting for more than 24 hours: defined as injection site reactions persisting for more than 24 hours and the severity is CTCAE Grade ≥ 3 .
- Parasitic and opportunistic infections: whether the infection is classified as opportunistic infection will be determined after discussion with medical monitor.

When reporting opportunistic infection, the Investigators will refer to [Appendix J Table 7](#).

- Anaphylaxis: defined according to the symptoms shown in [Appendix J Table 8](#).

11.3.4. Suspected Drug-induced Liver Injury

DILI refers to a liver injury induced by various chemical drugs, biological products, herbal medicines and their metabolites or even excipients. Hy's Law can facilitate assessment of severe liver injury predominated by hepatocellular injury. It specifically refers to cases that meet all of the following 3 criteria:

For participants with normal liver function tests at baseline:

1. ALT or AST $\geq 3 \times$ ULN during Treatment Assessment Period, and
2. Total bilirubin $> 2 \times$ ULN during Treatment Assessment Period; without cholestasis at baseline (serum alkaline phosphatase [ALP] increased), and
3. No other identifiable causes explaining the simultaneous elevation of aminotransferases and total bilirubin, such as viral hepatitis A, B, C or E or other acute liver diseases, or concomitant use of other drugs that may induce liver injury.

11.3.5. Unanticipated Adverse Device Effect

According to 21 CFR 812.3(s), a UADE means any serious adverse effect on health or safety or any life-threatening problem or death caused by, or associated with, a device, if that effect, problem, or death was not previously identified in nature, severity, or degree of incidence in the investigational plan or application (including a supplementary plan or application), or any other unanticipated serious problem associated with a device that relates to the rights, safety, or welfare of participants.

11.3.6. Unexpected Adverse Event

An AE that is not listed in the IB at the specificity or severity that has been observed. For example, hepatic necrosis would be unexpected (by virtue of greater severity) if the IB referred only to elevated hepatic enzymes or hepatitis. Similarly, cerebral thromboembolism and cerebral vasculitis would be unexpected (by virtue of greater specificity) if the IB listed only cerebral vascular accidents. This includes AEs that are mentioned in the IB as occurring with a class of products or as anticipated from the pharmacological properties of the IP but are not specifically mentioned as occurring with the particular IP under investigation.

11.4. Relationship to Investigational Product

The Investigator will assess the relationship of each AE to IP based on his/her clinical judgment. The causality assessment is one of the criteria used when determining regulatory reporting requirements. The Investigator's assessment of an AE's relationship to IP is part of the documentation process, but it is not a factor in determining what is or is not reported in the trial. The Investigator will assess causality for every event before entering information into the AE eCRF/Safety Reporting Form. The Investigator may change his or her opinion of causality in light of follow-up information and amend the AE/SAE information accordingly in the eCRF or

the AE eCRF/Safety Reporting Form, as applicable. The Sponsor's assessment of relationship may differ from the Investigator's assessment.

Relationship to IP will be assessed according to the following guidelines:

- Possibly related: the AE is known to occur with the IP, there is a reasonable possibility that the IP caused the AE, or there is a temporal relationship between the IP and event. Reasonable possibility means that there is evidence to suggest a causal relationship between the IP and the AE.
- Unlikely related: there is not a reasonable possibility that the administration of the IP caused the event, there is no temporal relationship between the IP and event onset, or an alternate etiology has been established.

11.5. Severity Assessment

It is important to distinguish between serious and severe AEs. Severity is a measure of intensity whereas seriousness is defined by the criteria under Section 11.3.2. An AE of severe intensity may not be considered serious.

The Investigator may use the CTCAE Version 5.0 to assist in the determination of severity and clinical significance. The following represents CTCAE grading of AE severity:

- Grade 1: asymptomatic or mild symptoms or clinical or diagnostic observations only or intervention not indicated.
- Grade 2: minimal, local or noninvasive intervention indicated or limiting age-appropriate instrumental activities of daily living (ADL). Instrumental ADL refers to preparing meals, shopping for groceries or clothes, using the telephone, managing money, etc.
- Grade 3: hospitalization or prolongation of hospitalization indicated or disabling or limiting self-care ADLs. Self-care ADLs refer to bathing, dressing and undressing, feeding self, using the toilet, taking medications and not bedridden.
- Grade 4: Life-threatening consequences with urgent intervention indicated.
- Grade 5: Death related to AE.

